**Figure 173: Infant Cytokines Over Time by Treatment Group – IL-5, IL-6, IL-7, and IL-8 – Infant Per Protocol Population**

[figure not shown]
**Figure 174: Infant Cytokines Over Time by Treatment Group – TNF- $\alpha$ , and TNF- $\beta$  – Infant Per Protocol Population**

**Figure 175: Maternal Cytokines Over Time by Treatment Group – IFN- $\gamma$ , IL-10, IL-12p70, and IL-12/IL-23p40 – Maternal Intent-to-Treat Population**

**Figure 176: Maternal Cytokines Over Time by Treatment Group – IL-13, IL-15, IL-16, and IL-17A – Maternal Intent-to-Treat Population**

**Figure 177: Maternal Cytokines Over Time by Treatment Group – IL-1 $\alpha$ , IL-1 $\beta$ , IL-2, and IL-4 – Maternal Intent-to-Treat Population**

**Figure 178: Maternal Cytokines Over Time by Treatment Group – IL-5, IL-6, IL-7, and IL-8 – Maternal Intent-to-Treat Population**

**Figure 179: Maternal Cytokines Over Time by Treatment Group – TNF- $\alpha$ , and TNF- $\beta$  – Maternal Intent-to-Treat Population**

Figures with similar format:

**Figure 180: Maternal Cytokines Over Time by Treatment Group – IFN- $\gamma$ , IL-10, IL-12p70, and IL-12/IL-23p40 – Maternal Per Protocol Population**

**Figure 181: Maternal Cytokines Over Time by Treatment Group – IL-13, IL-15, IL-16, and IL-17A – Maternal Per Protocol Population**

[figure not shown]
**Figure 182: Maternal Cytokines Over Time by Treatment Group – IL-1 $\alpha$ , IL-1 $\beta$ , IL-2, and IL-4 – Maternal Per Protocol Population**

[figure not shown]
**Figure 183: Maternal Cytokines Over Time by Treatment Group – IL-5, IL-6, IL-7, and IL-8 – Maternal Per Protocol Population**

[figure not shown]
**Figure 184: Maternal Cytokines Over Time by Treatment Group – TNF- $\alpha$ , and TNF- $\beta$  – Maternal Per Protocol Population**

[figure not shown]
Figures with similar format:

[figure not shown]
**Figure 185: GMC and 95% CI of Infant Cytokines Over Time by Treatment Group – IFN- $\gamma$ , IL-10, IL-12p70, and IL-12/IL-23p40 – Infant Intent-to-Treat Population**

**Figure 186: GMC and 95% CI of Infant Cytokines Over Time by Treatment Group – IL-13, IL-15, IL-16, and IL-17A -- Infant Intent-to-Treat Population**

**Figure 187: GMC and 95% CI of Infant Cytokines Over Time by Treatment Group -- IL-1 $\alpha$ , IL-1 $\beta$ , IL-2, and IL-4 --Infant Intent-to-Treat Population**

**Figure 188: GMC and 95% CI of Infant Cytokines Over Time by Treatment Group – IL-5, IL-6, IL-7, and IL-8 – Infant Intent-to-Treat Population**

**Figure 189: GMC and 95% CI of Infant Cytokines Over Time by Treatment Group –TNF-  $\alpha$ , and TNF-  $\beta$  – Infant Intent-to-Treat Population**

Figures with similar format:

[figure not shown]
**Figure 190: GMC and 95% CI of Infant Cytokines Over Time by Treatment Group – IFN- $\gamma$ , IL-10, IL-12p70, and IL-12/IL-23p40 – Infant Per Protocol Population**

[figure not shown]
**Figure 191: GMC and 95% CI of Infant Cytokines Over Time by Treatment Group – IL-13, IL-15, IL-16, and IL-17A -- Infant Per Protocol Population**

[figure not shown]
**Figure 192: GMC and 95% CI of Infant Cytokines Over Time by Treatment Group -- IL-1 $\alpha$ , IL-1 $\beta$ , IL-2, and IL-4 --Infant Per Protocol Population**

[figure not shown]
**Figure 193: GMC and 95% CI of Infant Cytokines Over Time by Treatment Group – IL-5, IL-6, IL-7, and IL-8 – Infant Per Protocol Population**

[figure not shown]
**Figure 194: GMC and 95% CI of Infant Cytokines Over Time by Treatment Group – TNF-  $\alpha$ , and TNF-  $\beta$  – Infant Per Protocol Population**

**Figure 195: GMC and 95% CI of Maternal Cytokines Over Time by Treatment Group – IFN- $\gamma$ , IL-10, IL-12p70, and IL-12/IL-23p40 – Maternal Intent-to-Treat Population**

**Figure 196: GMC and 95% CI of Maternal Cytokines Over Time by Treatment Group – IL-13, IL-15, IL-16, and IL-17A -- Maternal Intent-to-Treat Population**

**Figure 197: GMC and 95% CI of Maternal Cytokines Over Time by Treatment Group - IL-1 $\alpha$ , IL-1 $\beta$ , IL-2, and IL-4 -- Maternal Intent-to-Treat Population**

**Figure 198: GMC and 95% CI of Maternal Cytokines Over Time by Treatment Group –IL-5, IL-6, IL-7, and IL-8 – Maternal Intent-to-Treat Population**

**Figure 199: GMC and 95% CI of Maternal Cytokines Over Time by Treatment Group –TNF- $\alpha$ , and TNF- $\beta$  – Maternal Intent-to-Treat Population**

Figures with similar format:

[figure not shown]
**Figure 200: GMC and 95% CI of Maternal Cytokines Over Time by Treatment Group – IFN- $\gamma$ , IL-10, IL-12p70, and IL-12/IL-23p40 – Maternal Per Protocol Population**

**Figure 201: GMC and 95% CI of Maternal Cytokines Over Time by Treatment Group – IL-13, IL-15, IL-16, and IL-17A -- Maternal Per Protocol Population**

**Figure 202: GMC and 95% CI of Maternal Cytokines Over Time by Treatment Group - IL-1 $\alpha$ , IL-1 $\beta$ , IL-2, and IL-4 -- Maternal Per Protocol Population**

**Figure 203: GMC and 95% CI of Maternal Cytokines Over Time by Treatment Group –IL-5, IL-6, IL-7, and IL-8 – Maternal Per Protocol Population**

**Figure 204: GMC and 95% CI of Maternal Cytokines Over Time by Treatment Group –TNF-  $\alpha$ , and TNF-  $\beta$  – Maternal Per Protocol Population**

**Figure 205: Change from Baseline by Cytokine, Time Point, and Treatment Group — IFN- $\gamma$ , IL-10, IL-12p70, and IL-12/IL-23p40 – Infant Intent-to-Treat Population**

Figures with similar format:

**Figure 206: Change from Baseline by Cytokine, Time Point, and Treatment Group – IL-13, IL-15, IL-16, and IL-17A -- Infant Intent-to-Treat Population**

**Figure 207: Change from Baseline by Cytokine, Time Point, and Treatment Group -- IL-1 $\alpha$ , IL-1 $\beta$ , IL-2, and IL-4 -- Infant Intent-to-Treat Population**

**Figure 208: Change from Baseline by Cytokine, Time Point, and Treatment Group –IL-5, IL-6, IL-7, and IL-8 – Infant Intent-to-Treat Population**

**Figure 209: Change from Baseline by Cytokine, Time Point, and Treatment Group –TNF-  $\alpha$ , and TNF-  $\beta$  – Infant Intent-to-Treat Population**

[figure not shown]
**Figure 210: Change from Baseline by Cytokine, Time Point, and Treatment Group — IFN- $\gamma$ , IL-10, IL-12p70, and IL-12/IL-23p40 – Infant Per Protocol Population**

**Figure 211: Change from Baseline by Cytokine, Time Point, and Treatment Group – IL-13, IL-15, IL-16, and IL-17A -- Infant Per Protocol Population**

**Figure 212: Change from Baseline by Cytokine, Time Point, and Treatment Group -- IL-1 $\alpha$ , IL-1 $\beta$ , IL-2, and IL-4 -- Infant Per Protocol Population**

**Figure 213: Change from Baseline by Cytokine, Time Point, and Treatment Group –IL-5, IL-6, IL-7, and IL-8 – Infant Per Protocol Population**

**Figure 214: Change from Baseline by Cytokine, Time Point, and Treatment Group –TNF-  $\alpha$ , and TNF-  $\beta$  – Infant Per Protocol Population**

**Figure 215: Change from Baseline by Cytokine, Time Point, and Treatment Group — IFN- $\gamma$ , IL-10, IL-12p70, and IL-12/IL-23p40 — Maternal Intent-to-Treat Population**

Figures with similar format:

**Figure 216: Change from Baseline by Cytokine, Time Point, and Treatment Group – IL-13, IL-15, IL-16, and IL-17A -- Maternal Intent-to-Treat Population**

**Figure 217: Change from Baseline by Cytokine, Time Point, and Treatment Group -- IL-1 $\alpha$ , IL-1 $\beta$ , IL-2, and IL-4 -- Maternal Intent-to-Treat Population**

**Figure 218: Change from Baseline by Cytokine, Time Point, and Treatment Group – IL-5, IL-6, IL-7, and IL-8 – Maternal Intent-to-Treat Population**

**Figure 219: Change from Baseline by Cytokine, Time Point, and Treatment Group – TNF- $\alpha$ , and TNF- $\beta$  – Maternal Intent-to-Treat Population**

**Figure 220: Change from Baseline by Cytokine, Time Point, and Treatment Group — IFN- $\gamma$ , IL-10, IL-12p70, and IL-12/IL-23p40 – Maternal Per Protocol Population**

**Figure 221: Change from Baseline by Cytokine, Time Point, and Treatment Group – IL-13, IL-15, IL-16, and IL-17A -- Maternal Per Protocol Population**

**Figure 222: Change from Baseline by Cytokine, Time Point, and Treatment Group -- IL-1 $\alpha$ , IL-1 $\beta$ , IL-2, and IL-4 -- Maternal Per Protocol Population**

[figure not shown]
**Figure 223: Change from Baseline by Cytokine, Time Point, and Treatment Group – IL-5, IL-6, IL-7, and IL-8 – Maternal Per Protocol Population**

**Figure 224: Change from Baseline by Cytokine, Time Point, and Treatment Group – TNF- $\alpha$ , and TNF- $\beta$  – Maternal Per Protocol Population**

### 14.3.1.1 Solicited Adverse Events

[figure not shown]
**Figure 225: Maximum Severity of Solicited Systemic Symptoms per Subject by Day Post Treatment**

[Implementation Note: A sample Figure is shown below. For the CSR the Figure will include Pre-dose, post-dose and days 1, 2, 3, 4, 5, 6, 7 and 8 post dose. There will be a panel for BOOSTRIX, Td and All Subjects.]

**Figure 226: Maximum Severity of Solicited Local Symptoms per Subject by Day Post Treatment**

[figure not shown]
[Implementation Note: A sample Figure is shown below. For the CSR the Figure will include Pre-dose, post-dose and days 1, 2, 3, 4, 5, 6, 7 and 8 post dose. There will be a panel for BOOSTRIX, Td and All Subjects.]

### 14.3.1.2 Unsolicited Adverse Events

[figure not shown]
**Figure 227: Frequency of Related Adverse Events by MedDRA System Organ Class and Severity**

[Implementation Note: A sample Figure is shown below. There will be a panel for BOOSTRIX, Td and All Subjects.]

[figure not shown]
**Figure 228: Incidence of Related Adverse Events by MedDRA® System Organ Class and Maximum Severity**

[Implementation Note: A sample Figure is shown below. There will be a panel for BOOSTRIX, Td and All Subjects.]

[figure not shown]
**Figure 229: Frequency of Pregnancy-Related Adverse Events by MedDRA System Organ Class and Severity – Maternal Subjects**

[Implementation Note: A sample Figure is shown below. There will be a panel for BOOSTRIX, Td and All Subjects. This Figure will summarize pregnancy-related symptoms.]

[figure not shown]
**Figure 230: Incidence of Pregnancy-Related Adverse Events by MedDRA System Organ Class and Maximum Severity – Maternal Subjects**

[Implementation Note: A sample Figure is shown below. There will be a panel for BOOSTRIX, Td and All Subjects. This Figure will summarize pregnancy-related symptoms.]

[figure not shown]
**Figure 231: Frequency of Infancy-Related Adverse Events by MedDRA System Organ Class and Severity – Infant Subjects**

[Implementation Note: A sample Figure is shown below. There will be a panel for BOOSTRIX, Td and All Subjects. The Figure will summarize infancy-related symptoms.]

**Figure 232: Incidence of Infancy-Related Adverse Events by MedDRA System Organ Class and Maximum Severity – Infant Subjects**

[Implementation Note: A sample figure is shown below. There will be a panel for BOOSTRIX, Td and All Subjects. The figure will summarize infancy-related symptoms.]

[figure not shown]

#### **14.3.5 Displays of Laboratory Results**

Not Applicable.

### **16.1.6 Listing of Subjects Receiving Investigational Product**

(not included in SAP, but this is a placeholder for the CSR)

**16.2 Database Listings by Subject****16.2.1 Discontinued Subjects****Listing 1: 16.2.1 Early Terminations**

Treatment Group	Maternal/Infant	Subject ID	Reason for Early Termination	Study Day

## 16.2.2 Protocol Deviations

### Listing 2: 16.2.2.1: Subject-Specific Protocol Deviations

Treatment Group	Maternal/ Infant	Subject ID	DV Number	Deviation	Deviation Category	Study Day	Reason for Deviation	Deviation Resulted in AE?	Deviation Resulted in Subject Termination?	Deviation Affected Product Stability?	Deviation Resolution	Comments

**Listing 3: 16.2.2.2: Non-Subject-Specific Protocol Deviations**

Start Date	Deviation	End Date	Reason for Deviation	Deviation Resulted in Subject Termination?	Deviation Affected Product Stability?	Deviation Category	Deviation Resolution	Comments

**16.2.3 Subjects Excluded from the Efficacy Analysis****Listing 4: 16.2.3: Subjects Excluded from Analysis Populations**

Treatment Group	Maternal/Infant	Subject ID	Analyses in which Subject is Included	Analyses from which Subject is Excluded	Results Available?	Reason Subject Excluded
			[e.g., Safety, ITT, PP]	[e.g., Safety, ITT, PP, Day x]		

*Note: "Yes" in the "Results available" column indicates that available data were removed from the analysis. "No" indicates that no data were available for inclusion in the analysis.*

**16.2.4 Demographic Data****Listing 5: 16.2.4.1: Maternal Demographic Data**

Treatment Group	Subject ID	Age at Enrollment (years)	Ethnicity	Race	Other Ethnic Group	Gestational Age at Vaccination (weeks)

**Listing 6: 16.2.4.2: Infant Demographic Data**

Treatment Group	Subject ID	Sex	Gestation Age (weeks)	Ethnicity	Race	Other Ethnic Group	Delivery	Apgar Score (1, 5, 10 Minutes)	Birth Weight (kg)	Length at Birth (cm)	Head Circumference at Birth (cm)

**Listing 7: 16.2.4.2: Pre-Existing and Concurrent Medical Conditions**

Treatment Group	Subject ID	Maternal/Infant	MH Number	Medical History Term	Condition Start Day	Condition End Day	MedDRA System Organ Class	MedDRA Preferred Term

**16.2.5 Compliance and/or Drug Concentration Data (if available)**

Not Applicable.

**16.2.6 Individual Immunogenicity Response Data****Listing 8: 16.2.6: Individual Immunogenicity Response Data (Antibody)**

Treatment Group	Subject ID	Maternal/Infant	Planned Time Point	Actual Study Day	Tdap/DTwP	Serum IgG/Serum IgA/Breast Milk	Antibody Tested	Titer

**Listing 9: 16.2.6: Individual Immunogenicity Response Data (Cytokine)**

Treatment Group	Subject ID	Maternal/Infant	Planned Time Point	Actual Study Day	Cytokine Tested	Result

**16.2.7 Adverse Events****Listing 10: 16.2.7.1: Solicited Events – Systemic Symptoms**

Treatment Group	Subject ID	Post Dose Day	Assessment a	Symptom	Severity	Attributed to Alternate Etiology? b	Alternate Etiology
			MA				
			Clinic				

a MA = Data reported by subject on the Memory Aid and reviewed by clinic staff and reported in Solicited Events eCRF.  
b Grade 3 events only.  
Note: Clinic = Data collected by clinic staff during physical exam or symptom assessment (treatment administration record, in-clinic assessment, etc.)

**Listing 11: 16.2.7.2: Solicited Events – Local Symptoms**

Treatment Group	Subject ID	Post Dose Day	Assessment a	Symptom	Severity
			MA		
			Clinic		

a MA = Data reported by subject on the Memory Aid and reviewed by clinic staff and reported in Solicited Events eCRF.  
Note: Clinic = Data collected by clinic staff during physical exam or symptom assessment (treatment administration record, in-clinic assessment, etc.)

**Listing 12: 16.2.7.3: Unsolicited Adverse Events**

Adverse Event	No. of Days Post Dose (Duration)	Severity	SAE?	Relationship to Study Treatment	NOCMC?	In Not Related, Alternative Etiology	Subject Discontinued Due to AE	Outcome	MedDRA System Organ Class	MedDRA Preferred Term
Treatment Group: , Subject ID: , AE Number:										
Comments:										
Treatment Group: , Subject ID: , AE Number:										
Comments:										
Note: For additional details about SAEs, see Table: 61.										

**Listing 13: 16.2.7.3: Pregnancy or Infancy Related Adverse Events**

Adverse Event	Severity	SAE?	Relationship to Study Treatment	If Not Related, Alternative Etiology	Subject Discontinued Due to AE	Outcome	MedDRA System Organ Class	MedDRA Preferred Term
Treatment Group: , Subject ID:, Maternal/Infant, AE Number:								
Comments:								
Treatment Group: , Subject ID: Maternal/Infant, AE Number:								
Comments:								
Note: For additional details about SAEs, see Table: 61 .								

### **16.2.8 Individual Laboratory Measurements**

Not Applicable.

**16.2.9 Vital Signs and Physical Exam Findings****Listing 14: 16.2.9.1: Maternal Subject Vital Signs**

Treatment Group	Subject ID	Planned Time Point	Actual Study Day	Temperature (°C)	Systolic Blood Pressure (mmHg)	Diastolic Blood Pressure (mmHg)	Heart Rate (beats/min)

**Listing 15: 16.2.9.1: Infant Subject Vital Signs**

Treatment Group	Subject ID	Planned Time Point	Actual Study Day	Axillary Temperature (°C)	Respiratory Rate (breaths/min)	Heart Rate (beats/min)

**Listing 16: 16.2.9.2: Physical Exam Findings**

Treatment Group	Subject ID	Maternal/Infant	Planned Time Point	Actual Study Day	Body System	Abnormal Finding	Reported as an AE? (AE Description; Number)

**16.2.10 Concomitant Medications****Listing 17: 16.2.10: Concomitant Medications**

Treatment Group	Subject ID	Maternal/Infant	CM Number	Medication	Medication Start Day	Medication End Day	Indication	Taken for an AE? (AE Description; Number)	Taken for a condition on Medical History? (MH Description; Number)	ATC Level 1 (ATC Level 2)

**16.2.11 Pregnancy Reports****Listing 18: 16.2.11.2: Pregnancy Reports – Gravida and Para**

Subject ID	Pregnancy Number	Gravida	Live Births									Spontaneous Abortion/ Miscarriage	Elective Abortions	Therapeutic Abortions	Major Congenital Anomaly with Previous Pregnancy?
			Extremely PB a	Very Early PB a	Early PB a	Late PB a	Early TB b	Full TB b	Late TB b	Post TB b	Still Births				

Note: Gravida includes the current pregnancy, para events do not.

a Preterm Birth  
b Term Birth

**Listing 19: 16.2.11.3: Pregnancy Reports – Live Birth Outcomes**

Subject ID	Pregnancy Number	Fetus Number	Pregnancy Outcome (for this Fetus)	Fetal Distress During Labor and Delivery?	Delivery Method	Gestational Age at Live Birth	Size for Gestational Age	Apgar Score, 1 minute	Apgar Score, 5 minutes	Congenital Anomalies?	Illnesses/ Hospitalizations within 1 Month of Birth?

Note: Congenital Anomalies are included in the Adverse Event listing.

**Listing 20: 16.2.11.4: Pregnancy Reports – Still Birth Outcomes**

Subject ID	Date of Initial Report	Fetus Number	Pregnancy Outcome (for this Fetus)	Fetal Distress During Labor and Delivery?	Delivery Method	Gestational Age at Still Birth	Size for Gestational Age	Cord pH	Congenital Anomalies?	Autopsy Performed?	If Autopsy, Etiology for Still Birth Identified?

**Listing 21: 16.2.11.5: Pregnancy Reports – Spontaneous, Elective, or Therapeutic Abortion Outcomes**

Subject ID	Date of Initial Report	Fetus Number	Pregnancy Outcome (for this Fetus)	Gestational Age at Termination	Abnormality in Product of Conception?	Reason for Therapeutic Abortion

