Congenital Anomalies: In this study, we will report as SAEs all major congenital anomalies known prior to a mother/infant dyad completing the study. These outcomes must occur following maternal vaccination during gestation or the perinatal period (within the first 5 days after delivery) but the diagnosis may be confirmed anytime during participation. We define “major congenital anomaly” as “defects that are present at birth and that have surgical, medical, or serious cosmetic significance.” [33]

The following list of problems are among the conditions reported in the US National Birth Defects registry and would be deemed as examples of major congenital anomalies:

anencephaly, spina bifida, encephalocele, anophthalmia, microphthalmia, cyanotic congenital heart diseases, cleft lip or palate, tracheoesophageal fistula, rectal stenosis, major limb deformities including shortening, gastroschisis, omphalocele, and diaphragmatic hernia. Some problems that are congenital anomalies but would be considered minor include most simple birthmarks, single transverse palmar creases, clinodactyly, umbilical hernias, post-axial polydactyly, ankyloglossia, and epicanthal folds.

Positional deformations, such as molding or overriding cranial sutures, metatarsus adductus, tibial torsion, and genu varum are not to be recorded as major congenital anomalies. Normal variants, such as minor anomalies of the pinna, supernumerary nipples, and penile torsion are also not major congenital anomalies. If major congenital anomalies are found prenatally, before enrollment, women will be excluded from participation. Many minor congenital anomalies will typically only be noted at or soon after birth.

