### 3.2. Endpoints

#### 3.2.1. Primary

##### Safety and Tolerability:

- Safety in pregnant women: Frequency and severity of study vaccine-related serious adverse events, and all SAEs in pregnant women from study vaccination through 6 months postpartum, description and comparison between those receiving BOOSTRIX and Td.
- Safety in pregnant women and fetuses/infants: Frequency and severity of adverse events specific to pregnancy, in pregnant women and their infants (as delineated in [Section 4.5.1](#) ), description and comparison between those receiving BOOSTRIX and Td.
- Tolerability in pregnant women: Frequency and severity of solicited injection site and systemic reactogenicity events from study vaccination until 7 days following vaccination (Day 8).
- Tolerability in pregnant women: Frequency and severity of all unsolicited non-serious AEs from day of study vaccination to Day 31, description and comparison between those receiving BOOSTRIX and Td.
- Safety in the infants: Frequency and severity of study vaccine-related serious adverse events, and all SAEs in infants from birth through 6 months of age, description and comparison between infants born to women vaccinated with BOOSTRIX and Td.

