## 5. SAMPLE SIZE CONSIDERATIONS

Based on the accrual rate for similar studies, it seems reasonable to expect that the sites will be able to enroll this study in a timely fashion. Prior experience suggests up to 15% of subjects may be excluded from the per protocol analysis for the primary immunogenicity outcome either because they were lost-to-follow-up or otherwise do not have data available following the study vaccination, or because they had a protocol deviation requiring their exclusion from the per protocol analysis.

The study is planned to enroll 200 pregnant women (133 BOOSTRIX, 67 Td) and their infants.

This will be one of the first studies of maternal Tdap vaccination in an African, low resource setting, and where infants received whole cell, rather than acellular pertussis vaccinations. Thus, this study is intended to obtain preliminary estimates of immune response in this setting; it is not designed to test a specific null hypothesis.

**Table 3** indicates the probability of observing one or more safety event, such as solicited injection site or systemic symptom, or an unsolicited adverse event of a particular type within a treatment arm.

In addition to safety, as a co-primary objective, the study will assess serum PT antibody at birth among infants whose mothers received a single dose of BOOSTRIX or Td, and as secondary and exploratory objectives, the study will assess maternal and infant humoral response to all vaccine antigens. Immune response will be measured by ELISA. **Table 4** presents the precision (95% confidence interval (CI)) available for estimating GMC of ELISA titers against the vaccine component using assumptions for GMC and standard deviation (SD) for maternal and infant response to Tdap from Munoz et al. [10] and infant response post third dose of primary DTwP vaccine series from Ladhani et al. [11]

**Table 5** presents the minimum difference in infant PT antibody GMC at birth between the Td and Tdap (BOOSTRIX) vaccination arms that would be detectable with 80% power. The assumed GMC and SD used for these calculations are based on the PT antibody GMC and SD observed at birth in infants whose mother received either Tdap or placebo vaccination during pregnancy, reported in Munoz et al. [10] The calculations are based on a two-sided two sample T-test to compare means, with alpha = 0.05.

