### **6.3.3. Safety Population**

The Safety Analysis population includes all pregnant women who received the study vaccination, and all infants born during the study.

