#### **9.5. Pregnancies**

Every attempt was made to follow subjects to completion of pregnancy to document the outcome, including information regarding any complications with pregnancy and/or delivery. A table summarizing the total pregnancies, number of live births, and number of spontaneous abortions, elective abortions or still births by treatment group will be presented ([Table 75](#)). In addition, a listing of pregnancies and outcomes will be presented ([Listing 18](#), [Listing 19](#), [Listing 20](#), and [Listing 21](#)). A summary of infant size for gestational age at birth by treatment group will be presented in [Table 76](#) and [Figure 233](#).

Pregnancy related adverse events will be collected throughout the study and graded on a scale of 0 (absent), 1 (mild), 2 (moderate) and 3 (severe). Pregnancy related maternal events include pregnancy loss, bleeding during pregnancy or labor, postpartum hemorrhage, postabortal endometritis/salpingitis, preterm rupture of membranes, preterm contractions/labor/delivery, poor fetal growth, hypertension/preeclampsia/eclampsia, chorioamnionitis, postpartum endometritis, gestational diabetes and other pregnancy related AE. Infant events include preterm birth, birth weight, neonatal complications in a term infant, other AE in newborn and congenital abnormality/birth defect ([Table 8](#)).

The proportion of subjects reporting at least one pregnancy related adverse event will be summarized for each pregnancy related adverse event, any maternal symptom, and any infant symptom. The 95% CI will be calculated using Clopper-Pearson methodology from a binomial distribution (SAS Proc Freq with a binomial

(exact) option) will be presented ([Table 77](#) and [Table 78](#)). A Fisher's exact test w the difference in the proportion of subjects reporting a pregnancy related adverse event ([Table 79](#) and [Table 80](#)).

For each pregnancy related event, any maternal event, and any infant event, the maximum severity will be summarized for the maternal and infant Safety populations. The number and percentage of subjects reporting each event will be summarized by the maximum severity and treatment group. ([Table 81](#) and [Table 82](#)). The frequency of pregnancy- and infancy-related adverse events are presented in a bar chart in [Figure 229](#) and [Figure 231](#). The incidence of pregnancy- and infancy-related AEs are presented in [Figure 230](#) and [Figure 232](#).

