**Table 76: Summary of Infant Size for Gestational Age at Birth**

Size	BOOSTRIX (N=X)			Td (N=X)			All Subjects (N=X)		
	n	%	95% CI	n	%	95% CI	n	%	95% CI
Small for Gestational Age	x	xx	x.x, x.x	x	xx	x.x, x.x	x	xx	x.x, x.x
Appropriate for Gestational Age									
Large for Gestational Age									

Note: N= Number of subjects in the Infant Safety Population

**Table 77: Number and Percentage of Maternal Subjects Experiencing Pregnancy-Related Adverse Events with 95% Confidence Intervals by Symptom and Treatment Group**

Symptom	BOOSTRIX (N=X)			Td (N=X)			All Subjects (N=X)		
	n	%	95% CI	n	%	95% CI	n	%	95% CI
Any Maternal Pregnancy Related Symptom	X	XX	X.X, X.X	X	XX	X.X, X.X	X	XX	X.X, X.X
Pregnancy Loss									
Bleeding									
Postpartum Hemorrhage									
Postabortal Endometritis/Salpingitis									
Preterm Rupture of Membranes									
Preterm Contractions/Labor/Delivery									
Poor Fetal Growth									
Hypertension, Preeclampsia/Eclampsia									
Chorioamnionitis									
Postpartum Endometritis									
Gestational Diabetes									
Other Pregnancy Related AE									
Note: N= Number of subjects in the Maternal Safety Population									

**Table 78: Number and Percentage of Infant Subjects Experiencing Infancy-Related Adverse Events with 95% Confidence Intervals by Symptom, and Treatment Group**

Symptom	BOOSTRIX (N=X)			Td (N=X)			All Subjects (N=X)		
	n	%	95% CI	n	%	95% CI	n	%	95% CI
Any Neonatal and Infant Events	x	xx	x.x, x.x	x	xx	x.x, x.x	x	xx	x.x, x.x
Preterm Birth									
Birth Weight									
Neonatal Complications in a Term Infant									
Other AE in Newborn									
Congenital Abnormalities/Birth Defects									

Note: N= Number of subjects in the Infant Safety Population

**Table 79: Comparison of the Proportion of Maternal Subjects Experiencing Pregnancy-Related Adverse Events by Symptom and Treatment Group**

Symptom	Statistic	BOOSTRIX (N=X)	Td (N=X)
Any Maternal Pregnancy Related Symptom	Proportion (95% CI)	x.xx (x.xx, x.xx)	x.xx (x.xx, x.xx)
	Difference (95% CI)	NA	x.xx (x.xx, x.xx)
	p-value*	NA	0.xxx
Pregnancy Loss	Proportion (95% CI)		
	Difference (95% CI)		
	p-value*		
Bleeding	Proportion (95% CI)		
	Difference (95% CI)		
	p-value*		
Postpartum Hemorrhage	Proportion (95% CI)		
	Difference (95% CI)		
	p-value*		
Postabortal endometritis/salpingitis	Proportion (95% CI)		
	Difference (95% CI)		
	p-value*		
Preterm Rupture of Membranes	Proportion (95% CI)		
	Difference (95% CI)		
	p-value*		

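### The only by-arm anomaly rate is built on infants born, so a major anomaly in an aborted fetus, and possibly in a stillborn one, is not counted as an anomaly

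*SAP*

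**What the plan says.** Fetal and infant safety is a primary objective. The matching primary endpoint in SAP 3.2.1 is "Frequency and severity of adverse events specific to pregnancy, in pregnant women and their infants", to be described and compared between arms.

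- **Classification.** SAP 9.5 places anomalies on the infant side only: "Infant events include preterm birth, birth weight, neonatal complications in a term infant, other AE in newborn and congenital abnormality/birth defect". The maternal tables (77, 79 and 81) have no anomaly row.
- **Denominator.** The note under Table 78 reads "Note: N= Number of subjects in the Infant Safety Population", and Tables 80 and 82 use the same population. SAP 6.3.3 defines its infant part as "all infants born during the study".
- **Enrolment.** Protocol 7.4.2.2.1 enrols the newborn at birth. Table 12 takes enrolled infants as its base. Neither document says whether a stillborn is an infant of this population.
- **What is recorded for losses.** Listing 20 (stillbirths) has a field headed "Congenital Anomalies". Listing 21 (spontaneous, elective or therapeutic abortion) has "Abnormality in Product of Conception" and the reason for a therapeutic abortion.
- **Link to adverse events.** Listing 19 (live births) carries a note sending anomalies to the adverse event listing. Listings 20 and 21 carry no such note.
- **Serious adverse events.** Protocol 9.1 says that "we will report as SAEs all major congenital anomalies known prior to a mother/infant dyad completing the study", and brings anomalies arising in gestation after vaccination into scope.

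**The concern.** Vaccination takes place at 14 to 26 weeks, so whether the pregnancy ends in a live birth is itself a post-vaccination outcome. A rate computed only among infants born conditions on that outcome. If BOOSTRIX raised the frequency of anomalies severe enough to end the pregnancy, those cases would leave both the numerator and the denominator of the anomaly rate, and the anomaly contrast would lean toward no harm. The trial plans to list the information needed to avoid this, but no rule carries it into the comparison.

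**Working it through.** **1. Where a major anomaly counts, by pregnancy outcome**

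| Outcome | Recorded in | Counted by arm as an anomaly (Tables 78, 80, 82) | Counted by arm under another label |
|---|---|---|---|
| Live birth | Listing 19, with link to the AE listing | Yes | Infant SAE difference (Table 46) |
| Stillbirth | Listing 20 | Undefined | Pregnancy loss (Tables 77, 79, 81); Table 75, pooled with elective abortions; SAE |
| Spontaneous abortion | Listing 21 | No | Pregnancy loss; own row in Table 75; SAE |
| Elective abortion | Listing 21 | No | Pooled row in Table 75; pregnancy loss by row label only; SAE |
| Therapeutic abortion | Listing 21, with reason | No | No row in Table 75; pregnancy loss by row label only; SAE |

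The SAE entries assume that the event is reported as Protocol 9.1 requires. *By row label only* means that the pregnancy-loss row in SAP Table 8 covers any pregnancy not ending in a live birth, while its Grade 3 cell, the only grade available, names just spontaneous abortion or miscarriage.

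**2. The plan's own detection figure**

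Protocol Table 9 and SAP Table 3 give the chance of at least one event, 1 − (1 − p)^N. The arm sizes come from SAP 5: "The study is planned to enroll 200 pregnant women (133 BOOSTRIX, 67 Td) and their infants". At p = 1%:

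- BOOSTRIX: 1 − 0.99^133 = 73.7%
- Td: 1 − 0.99^67 = 49.0%

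Both match the printed values.

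**3. Anomalies omitted (assumed rates; the documents give none)**

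Assume loss after vaccination of 2–5%, a major anomaly in 5–20% of losses, and a major anomaly in 2–3% of live births. Treat stillborns as outside the infant population.

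- Omitted, BOOSTRIX: 133 × 0.02 × 0.05 = 0.13, up to 133 × 0.05 × 0.20 = 1.33
- Omitted, Td: 67 × 0.02 × 0.05 = 0.07, up to 67 × 0.05 × 0.20 = 0.67
- Counted, BOOSTRIX: 133 × 0.95 × 0.02 = 2.53, up to 133 × 0.98 × 0.03 = 3.91
- Share omitted, lowest: 0.133 / (0.133 + 3.910) = 3.3%
- Share omitted, highest: 1.33 / (1.33 + 2.527) = 34.5%

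The upper figure is a corner case: highest loss, highest anomaly rate among losses and lowest rate among live births. With loss 3%, anomaly in 10% of losses and in 2.5% of live births, the omitted number is 133 × 0.03 × 0.10 = 0.40. The counted number is 133 × 0.97 × 0.025 = 3.23, and the share is 0.40 / 3.63 = 11%.

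**4. Effect on seeing at least one anomaly in the anomaly row**

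Let q be the share of anomalies that end in loss or termination. The chance becomes 1 − (1 − p(1 − q))^N.

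| p | q | N = 133 | N = 67 |
|---|---|---|---|
| 1% | 0 | 73.7% | 49.0% |
| 1% | 10% | 70.0% | 45.4% |
| 1% | 25% | 63.3% | 39.6% |
| 2% | 0 | 93.2% | 74.2% |
| 2% | 25% | 86.6% | 63.7% |

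**5. Effect on the Fisher test**

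With 0 of 67 in Td, two-sided p first falls below 0.05 at 9 of 133 in BOOSTRIX (p = 0.030). One omitted case will seldom change that test. The loss is mainly in the estimate, its interval and the completeness of the description.

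**The case against.** The strongest reply is that these pregnancies are already compared between arms. Pregnancy loss is a graded pregnancy-specific event, so it falls within the primary endpoint, with a Clopper-Pearson interval and a Fisher test on the Maternal Safety Population. Table 75 gives outcomes by arm. Major anomalies are SAEs, and Tables 45 and 46 give SAE differences by arm. Table 62 lists major anomalies with treatment group and a maternal/infant column, and nothing restricts it to live births. Protocol 11.4.2 adds a Fisher comparison covering untoward fetal outcomes if more than 5% of women (more than 10 of 200) are affected.

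This stands against the broader inference that a reader might draw, namely that lethal or terminated anomalies never reach the primary safety comparison or appear only in listings. The documents do not support it. They also do not support saying that a stillborn is excluded: the definition turns on being born during the study, and the status is undefined.

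These routes do not close the narrower gap. They count a loss or an SAE, and an anomaly signal is diluted among unrelated losses and SAEs. Table 62 has no rate or interval, and the plan does not say whether mother or infant carries the event.

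Two further points have weight. First, an abnormality in Listing 21 is not automatically a major congenital anomaly, which Protocol 9.1 defines by presence at birth. The protocol schedules no fetal examination after a loss, so unexamined fetuses would count as unaffected. This limits the new row and is a reason to keep the infant row beside it. Second, few anomalies are expected, known or suspected major anomalies are excluded at entry (exclusion 18), and the study tests no specific null hypothesis. This limits the size of the problem but not the need for a complete by-arm description.

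**Conclusion.** The concern holds for the anomaly-specific comparison only. Every by-arm anomaly rate rests on infants born. An anomaly in an aborted fetus is outside it, and one in a stillborn may be, although the trial plans to list both. The gap is widest for elective and therapeutic terminations, where the alternative count as pregnancy loss is itself unclear.

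The size is illustrative. Under the assumed rates in the working, about 0.1 to 1.3 anomalies are omitted in the BOOSTRIX arm, or 3% to 35% of that arm's anomalies, with the upper end a corner case. If stillborns are in fact counted as infants born, the numbers are smaller. The bias toward no harm arises only if the vaccine raises anomalies that end the pregnancy, and in that case the pregnancy-loss row could still show an excess. The change is worth making because the endpoint is primary and the fields are already planned. It does not mean that the primary safety comparison as a whole misses these pregnancies.

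**What to change.** - **New row.** Keep the infant rows. Add to Tables 78 and 80 a by-arm row for major congenital anomaly per fetus of vaccinated women with known pregnancy outcome, with its own printed denominator, Clopper-Pearson interval and Fisher test. Count live births, stillbirths (Listing 20) and spontaneous, elective or therapeutic abortions (Listing 21) where the abnormality is one of the major anomalies set out in Protocol 9.1. Enrolment requires a singleton, so fetus and pregnancy should coincide.
- **Ascertainment.** Report by arm how many lost fetuses were examined. Listing 20 has an autopsy field. The Listing 21 shell shows no equivalent, so the source for abortions must be named.
- **Rules.** Say in SAP 6.3.3 whether a stillborn belongs to the Infant Safety Population. State that anomalies in lost fetuses appear in Table 62, and whether mother or infant carries them.
- **Listings.** Add treatment group to Listings 20 and 21. SAP 9 sorts listings by treatment group, but these shells have no such column.

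The cost is SAP text, one row in each of two tables, one column in each of two listings, and a decision for each reported abnormality on whether it is major. The anomaly fields themselves are already planned. The drawback is less complete ascertainment in unexamined losses, so the two rows should be read together.
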